12. DATA AND SPECIMEN BANKING*

N/A

13. Data Analysis and Management*

Power calculations were based off findings from Garcia et al. which showed a mean difference of 12 between telephone and translator nursing satisfaction scores. In their study patients' satisfaction was evaluated looking specifically looking at three main subcategories, nursing, physician, and interpreter satisfaction. Sample size calculations were based off seeing a minimum of 12-point difference between mean scores for nursing satisfaction. Our sample size is of sufficient enough size to detect a meaningful difference between mean scores of the other two subcategories as well. We calculated an initial sample size of 48 with a significance level of 5% and power of 80%. Taking into consideration data analysis with multivariate linear regression analysis we added 10 additional participants per variable (Expected dependent variables include: English fluency, interpreter service experience, language, and age)

INVESTIGATOR STUDY PLAN

48 +(10 x 4) = 88. Based on our patient population and taking into consideration potential conflicts that could arise with patients cancelling follow up appointments we are expecting a 30% drop out rate. This gave us to a final total sample size of 114 (57 each arm)

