4. OBJECTIVES*

Primary Objective: To determine if In-person interpreters increases patient satisfaction of Urogynecological(URGYN) office visits compared to the use of phone interpreter services for Limited English Proficient (LEP) patients

Secondary Objective: To determine if type of provider, years spent in the US, income level, or level of education influences patient satisfaction of UROGYN office visits

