10. STUDY ENDPOINTS*

The primary outcome, patient satisfaction will be measured by a fourteen-item questionnaire previously used and internally validated by Garcia et al. The questionnaire has 3 sections that evaluates satisfaction with the interpreter, provider, and nurse. We will be assessing the interpreter satisfaction section scores of each subcategory as well as the overall score. All items are answered on a scale of 1 to 4 and weighted on a 100 - point scale.

Secondary outcomes evaluate patient satisfaction in relation to type of provider, years spent in the US, income level, and level of education.

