21. SHARING OF RESEARCH RESULTS WITH SUBJECTS*

Subjects will not be notified of the results. Questionnaires will be scored once all data has been collected and entered into the database.

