22. SETTING

Subjects will be identified and recruited in the urogynecology clinic located in two locations, UMass Memorial and Northborough UMass Memorial Health Care. The urogynecology division has two full-time designated surgeons (including the PI) and both will participate in the study. In addition, the nurse practitioner and department fellows will work as co-PI and study assistants. This comprises the team who will recruit subjects and obtain intraoperative and postoperative study data.

Data entry and analysis will be performed in the administrative offices of the division on Jaquith 2 in U Mass Memorial.

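### Does the secondary objective need a named score, a model, a multiplicity rule and a provider-level analysis before it can be answered?

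*Combined protocol and SAP*

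**What the plan says.** The secondary objective in section 4 is "To determine if type of provider, years spent in the US, income level, or level of education influences patient satisfaction". Section 10 repeats the same four factors: "Secondary outcomes evaluate patient satisfaction in relation to type of provider, years spent in the US, income level, and level of education". Neither section names a score, a coding of the factors, a model or a rule for multiple tests.

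On the scores, section 10 states "The questionnaire has 3 sections that evaluates satisfaction with the interpreter, provider, and nurse" and then "We will be assessing the interpreter satisfaction section scores of each subcategory as well as the overall score". The second sentence can be read as all three section scores plus the overall score, or as the interpreter section plus the overall score.

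Section 13 names multivariate linear regression as the reason for adding 10 participants per variable, with an open list: "Expected dependent variables include: English fluency, interpreter service experience, language, and age".

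On staffing, section 22 says "The urogynecology division has two full-time designated surgeons (including the PI) and both will participate in the study", and that "the nurse practitioner and department fellows will work as co-PI and study assistants". The number of fellows is not given, and no section defines the categories of provider type.

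On timing, section 21 says "Questionnaires will be scored once all data has been collected and entered into the database".

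**The concern.** A reader who looks for the analysis of the secondary objective finds none tied to it. The one regression in the document lists four other variables and labels them with the word for an outcome. Two consequences seem to go beyond missing wording.

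- **Multiplicity.** With four factors, up to four scores and no score designated, a report could pick out whichever pair reaches p < 0.05 and call that factor an influence on satisfaction.
- **Provider type.** Section 22 speaks of one nurse practitioner. If type of provider means nurse practitioner against surgeon, the effect of the type and the effect of that one person are the same quantity, however many patients are enrolled. An ordinary regression would treat each of her patients as independent evidence about the type, so its p-value would be too small.

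At stake is a false or over-read secondary claim about what drives satisfaction.

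**Working it through.** **Sample available.** The plan's own figure comes first: 48 + (10 × 4) = 88, and 88 × 1.30 = 114.4, which gives the stated 114. With the 30% dropout that section 13 expects, 114 × 0.70 = 79.8, or about 80 completers. Whether 114 is enough to keep 88 is a separate matter.

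**Overlap of variables.** The secondary factors are provider type, years in US, income and education. Section 13 lists English fluency, interpreter service experience, language and age. The overlap is 0 of 4. The list is introduced as what is expected to be included, so it does not exclude the secondary factors. The listed items are patient characteristics, and the allowance of 10 per variable is a rule for predictors, so 'dependent' is a slip.

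**Number of tests.** The plan gives no count. One test per factor and score gives:
- broad reading of section 10: 4 × 4 = 16 tests, with 16 × 0.05 = 0.8 expected false positives if no factor matters;
- narrow reading: 4 × 2 = 8 tests, with 0.4 expected;
- one score: 4 tests, with 0.2 expected.

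**Chance of at least one p < 0.05 if no factor matters.** Under independence this is 1 − 0.95^k: 56.0% for k = 16, 33.7% for k = 8 and 18.5% for k = 4. Independence cannot hold across scores, because the overall score contains the sections. The correlated figures come from simulation with 80 patients, three normal section scores with correlation 0.3 to 0.8 (assumed), the overall score as their mean, four normal factors with correlation 0 to 0.5 (assumed), and arm in every model:

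| Scores tested | Tests | Simulated chance |
|---|---|---|
| three sections + overall | 16 | 29% to 46% |
| interpreter + overall | 8 | 21% to 29% |
| overall only | 4 | 15% to 19% |

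The simulation treats all four factors as continuous, although provider type is categorical.

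**Provider contrast.** Take one nurse practitioner with m patients against two surgeons with k patients each. Let ICC be the share of score variance lying between individual providers. In units of the total variance:
- variance assumed by ordinary regression: 1/m + 1/(2k);
- true variance: 1.5 × ICC + (1 − ICC) × [1/m + 1/(2k)].

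For m = k = 20 (assumed), the first is 1/20 + 1/40 = 0.075.
- ICC 0.01: 0.015 + 0.99 × 0.075 = 0.08925; ratio 1.19; true error of a nominal 5% test 7%.
- ICC 0.05: 0.075 + 0.95 × 0.075 = 0.14625; ratio 1.95; error 16%.
- ICC 0.10: 0.150 + 0.90 × 0.075 = 0.2175; ratio 2.90; error 25%.

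Other patient splits (m from 10 to 30, k from 13.5 to 20) give 6% to 29%. The documents supply neither an ICC nor patient numbers per provider, and the calculation leaves out the fellows.

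**Cost of modelling individual providers.** Two surgeons, one nurse practitioner and at least two fellows (section 22 uses the plural) make at least 5 providers, hence at least 4 indicator terms. Language, years in US, income and education, counted as one term each, bring this to at least 8 terms besides arm. At the plan's 10 per variable that calls for 80 added participants, where section 13 added 40. English fluency, interpreter experience and age would still be left out. Section 16 makes the income question optional, so the usable number could fall below 80.

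**The case for a change.** The strongest case for a change is that saying 'regression will be used' does not cure either problem. Regressing each score on the four factors still leaves many tests, and a one-person category cannot be identified as a type under any model or sample size. The remedy looks cheap: name one score, label the results exploratory, and record who saw each patient.

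Some of this stands. The document does leave the score and model open. If the report contrasts the nurse practitioner with the surgeons, it cannot attribute the difference to provider type, and that limit needs no assumption about the ICC. Any other grouping would still rest on few providers.

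The rest is weaker:
- Sixteen tests is a count made by a reader under the broad reading of section 10. On the narrow reading, naming one score moves the chance of a false lead only from 21%–29% to 15%–19%.
- One named score has a price. Provider type most plausibly acts on the provider section, and restricting the question to the overall score would dilute that.
- Provider type is undefined. If it were attending against non-attending, each group would hold several people and the one-person argument would not apply in that form.
- Adjusting for individual providers would turn a stated objective into description and would load the model beyond what section 13 allowed for.
- Doubt about whether years in the US is collected is speculative. The data forms are not in the document, and section 11 provides for demographic information at the follow-up visit.

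**Conclusion.** The omission is real but minor, and it does not call for a change to the plan. Sections 4 and 10 leave the score and model for the secondary factors open. Section 13 names a suitable class of model with an open list of covariates. A competent analyst would fit a linear regression with arm and the four factors, report estimates with confidence intervals, and present them as associations. Because section 21 puts scoring after data entry, those choices can be settled before any score is seen. 'Dependent' in section 13 is a clerical slip that would mislead no analyst.

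Leaving multiplicity uncontrolled for secondary associations that are never called confirmatory is a fair trade-off. The price is a 29% to 46% chance of at least one chance finding if all four scores are tested, or 21% to 29% with two, against 15% to 19% with one. These figures assume 80 completers and the stated correlations. The provider figures (7% to 25%, or 6% to 29% over other splits) illustrate one contrast under an assumed ICC and assumed patient numbers. They do not show that the plan contains an error of that size. The small number of providers is a limit on interpretation that no analysis choice removes.

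The randomised comparison of in-person with phone interpreters does not depend on any of this.

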11. PROCEDURES INVOLVED*

This study is a randomized controlled trial. Patients presenting to our UROGYN clinic will be screened for eligibility using inclusion and exclusion criteria.. LEP patients will be identified as patients that

INVESTIGATOR STUDY PLAN

initiate conversation in a non-English language and are only able to communicate adequately regarding their medical problem in a non-English language. This definition was adapted from a previously used technique to identify LEP patients as described by Gany et al.⁵

After patients, have been seen for their scheduled office visit they will be invited to participate in the study. Once the patient has agreed to participate in the study the participant will be randomized. Participants will be given ample time to read the fact sheet and given the opportunity to take the fact sheet home for further review if they choose. Participants must call to be enrolled prior to their next visit, because randomization will occur before the follow up visits. No randomization will occur at the follow-up visit. Patients cannot request to be enrolled at the time of the follow up visit. Study assignment will be revealed using sequentially numbered sealed opaque envelopes. Randomization will be performed using software and a block randomization scheme to yield a 50% chance of having an in-person interpreter.

Portuguese and Spanish LEP participants will be randomized from two separate blocks. Bilingual participants will be identified at that time and be asked the primary language they would like for medical interpreter services for the subsequent office visit. Those assigned to the control group will receive phone translation services and the experimental group will have in person interpreters. Once randomized, research team members will make a note in the computer scheduling system if an in-person interpreter is needed for the next visit.. At the subsequent visit, demographic information will be collected and patients will then receive interpretation services from the phone or an in-person interpreter.

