At completion of the follow up visit subjects will complete two forms, in their native language. The first form is a fourteen-item patient satisfaction questionnaire that has been previously used in published studies. The first form also has two questions from the Consumer Assessment of Healthcare Providers and System Hospital Survey (www.cahps.ahrq.gov). The second form will assess subjects English proficiency, overall health status, and yearly household income.

For eligible patients who decline participation we will be collecting non-identifiable information including; patient age, type of visit, language, provider, and if the patient was alone for the visit. This will provide us non-identifiable data for comparative analysis between the group of eligible patients who agreed to participate and those who declined.

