15. WITHDRAWAL OF SUBJECTS WITHOUT THEIR CONSENT*

We do not anticipate a situation where a subject would have to be removed from the study. A unique situation that could arise, is that a participant could become incarcerated prior to their follow up visit. Section # 18 details how this situation would be addressed. Moreover, should a situation arise, excluding a randomized subject from the study would not pose any harm to the subject. Subjects who fail to show for their follow-up visits will not be withdrawn from the study

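### The 30% drop-out allowance multiplies 88 by 1.30 instead of dividing by 0.70, so 114 randomised should yield about 80 participants with outcome data, 8 short of the plan's own 88

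*Combined protocol and SAP*

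**What the plan says.** All the sample size reasoning is in section 13 (Data Analysis and Management) of the combined protocol and SAP.

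- **Base size.** "We calculated an initial sample size of 48 with a significance level of 5% and power of 80"%. The planning difference is 12 points on the nursing satisfaction score. No standard deviation is given, and the section does not say whether 48 is a total or per arm.
- **Regression allowance.** For the planned multivariable model, "we added 10 additional participants per variable". Four variables are listed, so the target is 48 + (10 × 4) = 88.
- **Drop-out.** With cancelled follow-up appointments in mind, "we are expecting a 30% drop out rate. This gave us to a final total sample size of 114 (57 each arm"). The inflation formula is not shown.

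Sections 24 and 25 repeat 114 as the number to be recruited and enrolled.

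Two other sections fix when the loss occurs. Section 11 says that "randomization will occur before the follow up visits", and that "At completion of the follow up visit subjects will complete two forms, in their native language". Section 15 adds: "Subjects who fail to show for their follow-up visits will not be withdrawn from the study".

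**The concern.** A drop-out allowance should make the number left after the loss equal to the target. If a fraction *d* of those randomised is lost, the number to randomise is target / (1 − *d*). Multiplying the target by (1 + *d*) is a common slip. It always gives too few, because the loss applies to the inflated number and not to the target. The gap grows with *d*, and at 30% it is not negligible.

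Section 13 presents 114 as the number that allows for 30% drop-out from a requirement of 88. If it does not, the stated enrolment fails to meet the plan's own requirement under the plan's own assumption, and anyone judging recruitment against section 13 would expect 88 analysable participants. The participants at stake are those added for the regression, along with some precision. The basic two-group comparison is affected much less, provided 48 is a total.

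**Working it through.** **Inputs, all from section 13:** base size 48; regression allowance 10 × 4 = 40; target 48 + 40 = 88; drop-out 30%; stated size 114, or 57 per arm; significance level 5%, power 80%.

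**1. Reproducing the stated 114**

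| Rule | Calculation | Result |
|---|---|---|
| Target × (1 + *d*) | 88 × 1.30 | 114.4 |
| Same, per arm | 44 × 1.30 | 57.2 |
| Target / (1 − *d*) | 88 / 0.70 | 125.7, so 126 (63 per arm) |
| Inflate only the 48, by division | 48 / 0.70 + 40 | 108.6 |
| Inflate only the 48, by multiplication | 48 × 1.30 + 40 | 102.4 |

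Only multiplication of the whole target by 1.30 gives 114 and 57 per arm. The formula is inferred, since the plan does not print it. The shortfall below does not depend on that inference.

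**2. What 114 delivers at 30% drop-out**

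- Expected with outcome data: 114 × 0.70 = 79.8, or 57 × 0.70 = 39.9 per arm.
- Shortfall: 88 − 79.8 = 8.2, and 8.2 / 88 = 9%.
- Drop-out at which 114 still yields 88: 1 − 88/114 = 22.8%.
- Chance of 88 or more with outcome data, if losses are independent at 30%: P(Binomial(114, 0.70) ≥ 88) = 0.055. With 126 randomised it is 0.56.

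**3. Effect on the analysis**

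- Margin above the base size: 88 − 48 = 40 as planned, against 79.8 − 48 = 31.8 expected.
- Confidence interval width relative to 88: √(88 / 79.8) = 1.05.
- Power, assuming 48 is a total (24 per arm) and a two-sided 5% t-test: 80% power at 24 per arm implies a standardised difference of 0.826. At that difference, unadjusted power is 0.954 with 40 per arm and 0.969 with 44 per arm.
- Sensitivity, if 48 were per arm: power would be about 72% with 40 per arm and 76% with 44. This reading does not fit the sum to 88 or the 57 per arm.

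The 48 cannot be checked because no standard deviation is given. Steps 1 and 2 do not need one.

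**The case against.** The best counter-argument is that the slip hardly matters. On the likely reading of 48, power stays near 95% against a stated 80%. The 88 is a cushion built from a rule of thumb and not a derived requirement: about 80 participants is still 20 per covariate for four covariates, or 16 if treatment is counted as a fifth term. Falling from 88 to 80 crosses no threshold in the plan. That is fair as to size, and it is why the recommended fix adds no patients. It does not make the stated number right.

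A second argument is that section 15 keeps no-shows in the study, and a cancelled visit might be rescheduled and the forms completed then. Final loss could then be below 30%. But the plan describes no rescheduling for this purpose and no imputation, and keeping someone enrolled does not supply a questionnaire. The plan also calls 30% its drop-out rate. What stands is that 79.8 treats every drop-out as permanently without outcome data.

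A third argument is that the power figures are narrow. They are unadjusted and concern the nursing score used for planning, whereas section 10 names the interpreter section score, the subcategory scores and the overall score. That is correct. They show how little this particular error costs and give no general assurance about the primary outcome.

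**Conclusion.** The concern holds. At the stated 30% drop-out, 114 randomised is expected to give about 80 participants with outcome data (about 40 per arm), 8 or 9% short of the 88 that section 13 sets. The plan reaches 88 only if drop-out is 22.8% or lower.

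This rests on the plan's own figures and on one reading: a participant who drops out has no primary outcome, which follows from collecting the forms only at the follow-up visit. The statement that the powered comparison is not at risk rests on more: 48 being a total, a two-sided t-test, and the nursing score difference used for planning. The four-covariate model can still be fitted with about 80 participants. The number is wrong as written and should be corrected, but the error does not threaten the trial.

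**What to change.** In section 13, replace the last sentence with: *114 randomised (57 per arm) is expected to give about 80 participants with outcome data at 30% drop-out, or 88 if drop-out is no more than about 23%.* In the same place, state that 48 is the total for both arms, after confirming this against the team's own calculation. Keep all four planned covariates.

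The cost is a small text edit in section 13. There are no extra patients, no change to the analysis, and no change to sections 24 and 25.

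If the team would rather meet 88 at 30% drop-out, the consistent figure is 126 (63 per arm), with 126 × 0.70 = 88.2 expected. That means 12 more participants and matching edits to sections 13, 24 and 25. At the plan's own pace the extra recruitment time is 12 / (114/14) = 1.5 months on the 14-month estimate in section 9, or 12 / (114/17) = 1.8 months on the 17-month estimate in section 24.

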14. PROVISIONS TO MONITOR THE DATA TO ENSURE THE SAFETY OF SUBJECTS*

The datasheets will be kept in a locked cabinet in a locked office in the administrative offices of the division on Jaquith 2. The data will be entered into a de-identified, password protected file kept on the departmental computer servers.

15. WITHDRAWAL OF SUBJECTS WITHOUT THEIR CONSENT*

We do not anticipate a situation where a subject would have to be removed from the study. A unique situation that could arise, is that a participant could become incarcerated prior to their follow up visit. Section # 18 details how this situation would be addressed. Moreover, should a situation arise, excluding a randomized subject from the study would not pose any harm to the subject. Subjects who fail to show for their follow-up visits will not be withdrawn from the study

16. RISKS TO SUBJECTS*

This study poses minimal risk to subjects, there is the potential risk of embarrassment that the participant might feel with the question about household income. That is not the intent of the question, and the question is optional. Other items that could cause potential embarrassment are the patient satisfaction questionnaire, and questions regarding English proficiency and education level. These questions have been well thought out and written with care to try to avoid this.

There is no economic risk to the patient, as the medical interpreter service is not an additional fee for the patient. There is a risk of breach of confidentiality since protected health information is being collected. The datasheets will be kept in a locked cabinet in a locked office in the administrative offices of the division on Jaquith 2. The data will be entered into a de-identified, password protected file kept on the departmental computer servers.

